3.6.1.2 Clinical Laboratory Tests

Clinical laboratory safety tests including serum pregnancy tests will be performed in a central clinical laboratory. Urine pregnancy tests may be performed at the site using a licensed test (dipstick). Abnormal laboratory results that are considered clinically relevant by the investigator should be repeated as soon as possible (preferably within 24-48 hours). These repeat tests may either be performed by the central clinical laboratory or by a laboratory local to the site as clinically indicated. If the urine dipstick test is abnormal, with a result greater than negative or trace, then a urine microscopy and culture will be performed.

Laboratory measurements will be evaluated with descriptive statistics (N, mean, median, and standard deviation, minimum and maximum) for lab results and changes from baseline at each collection time point. All laboratory values will be included in the listings and values outside of the normal range will be flagged. Shift tables will be provided for Lab result. For laboratory values reported as lower than the limit of quantification (LLOQ), a value equal to half of the limit of quantification will be imputed in the summaries. However, all laboratory measurements will be included in the data listings as reported without any imputation.

The number and percent of patients with blood eosinophil counts >1500 cells/UL will be summarized by treatment group and by visit.

For presentation, change from baseline in blood eosinophil counts over time by treatment group will be plotted for both ITT population and PP population. Intra-patient variability for blood eosinophils will be evaluated during the run-in period (between Week -2 and Week 1 visits).

Summary	Population	Analysis
Hematology Results	Safety	Stage 1; Stage 2
Serum Chemistry Results	Safety	Stage 1; Stage 2
Change from Baseline in Hematology Results	Safety	Stage 1; Stage 2
Change from Baseline in Serum Chemistry Results	Safety	Stage 1; Stage 2

Shift Table for Hematology	Safety	Stage 1; Stage 2
Shift Table for Serum Chemistry	Safety	Stage 1; Stage 2
Number of Subjects with Blood Eosinophil Counts >1500 cells/UL	Safety	Stage 1; Stage 2
Intra-patient Variability for Blood Eosinophil Counts During the Run-in Period		Stage 1

3.6.1.3 Vital sign

Vital sign (blood pressure, temperature, pulse rate, and respiration rate) results and shift table for vital sign results will be summarized using descriptive statistics. In addition, listing of vital signs will be generated.

Summary	Population	Analysis
Vital Sign Results	Safety	Stage 1; Stage 2
Shift Table for Vital Sign Results	Safety	Stage 1; Stage 2

3.6.1.4 ECG

Computerized 12-lead ECG recordings will be obtained after the subject has been supine for at least 10 minutes. Each lead will be recorded for at least 3-5 beats at a speed of 25 mm/sec paper speed and 10 mm/mV amplitude. Heart rate, PR, QRS, QT and QTc intervals (msec) will be recorded from the 12-lead ECG. The principal investigator or a designated subinvestigator will be responsible for the overall interpretation and determination of clinical significance of any potential ECG findings. The ECG will also be transmitted to a central reader to quantitatively assess PR, QRS, QT, and QTc intervals.

The number of subjects with ECG results and the shift table for ECG results will be produced. In addition, the observed values for quantitative assessments (heart rate, PR, QRS, QT, and QTc intervals) and the change from baseline for QT and QTc intervals will be summarized with descriptive statistics. All ECG results will be presented in the data listing.

Summary	Population	Analysis
Number of Subjects With ECG Results	Safety	Stage 1; Stage 2

Shift Table for ECG Results	Safety	Stage 1; Stage 2
Summary of Quantitative ECG Results	Safety	Stage 1; Stage 2
Change from Baseline in Quantitative ECG Results	Safety	Stage 1; Stage 2

3.6.1.5 Physical Examination

All abnormal physical exam findings (pre and post-dose assessments) will be listed.

3.6.2 The Effect of Tralokinumab on Pulmonary Function

Spirometry testing must be performed in the morning between 6:00 and 11:00 AM according to the schedule of study procedures. On treatment days, spirometry testing will be performed before administration of investigational product. The following values will be captured: preand post-bronchodilator FEV₁, FEV₆, FVC, FEV₁/FVC, and IC.

Multiple forced expiratory efforts (at least 3 but no more than 8) will be performed for each clinic spirometry session and the 2 best efforts that meet the ATS/ERS acceptability and reproducibility criteria will be recorded. The best efforts will be based on the highest FEV₁. The maximum FEV₁ of the 2 best efforts will be used for the analysis. The absolute measurement (for FEV₁ and FVC), and the percentage of predicted normal value will be recorded using appropriate reference values. The highest FVC will also be reported regardless of the effort in which it occurred (even if the effort did not result in the highest FEV₁). Inspiratory capacity will be recorded using a slow spirometry manoeuvre; the best effort following a minimum of 3 IC measurements will be recorded. For the analyses of FEV₆, the highest value will be used. For FEV₁/FVC calculation, the highest FVC and the highest FEV₁ will be selected.

Reversibility is calculated based on the maximum pre- and post-bronchodilator FEV_1 as follows:

% Reversibility = (post-bronchodilator
$$FEV_1$$
- pre- bronchodilator FEV_1) × 100
pre-bronchodilator FEV_1

Spirometry measurements and reversibility as well as the changes from baseline and percent change from baseline will be summarized with descriptive statistics. ANCOVA may be used to compare the change from baseline with age, gender, number of exacerbations in past year

 $(2 \text{ vs} > 2 \text{ but} \le 6)$, atopic asthma status (absence/presence), chronic OCS use (presence versus absence) and geographical region as the potential covariates at Week 53 and Week 75

Home peak flow testing for FEV_1 and PEF will be performed twice daily, in the morning upon awakening and in the evening prior to bedtime from Visit 2 through the Week 75 visit using a PFM.

The weekly morning and evening average of FEV₁ and PEF at home will be summarized by week. The weekly average along with change from baseline and percent change from baseline at various time points will be summarized using descriptive statistics. Diurnal PEF variability defined as 100% x (PM PEF - AM PEF)/((AM PEF +PM PEF)/2), i.e. amplitude % mean will be summarized by visit using descriptive statistics also.

Spirometry data will be summarized for the following subgroups:

- 1) Subjects with percentage of predicted FEV1 at baseline $\leq 60\%$, and $\leq 80\%$;
- 2) Subjects with baseline % FEV1 reversibility (>= 12% and < 12%);
- Subjects with pre-bronchodilator FEV1 improvement at Week 5 and Week 13 (defined as percent change from baseline ≥ 10%) from tralokinumab group;
- 4) Subjects grouped by number of asthma exacerbations in the past year (2 vs > 2 but \leq 6 exacerbations);
- 5) Subject grouped by chronic OCS use (presence vs absence);
- 6) Subjects grouped by Th2 status (Th2-high vs Th2-low);
- 7) Subjects grouped by atopic asthma status (atopic vs. non-atopic);
- 8) Subjects grouped by baseline serum periostin level (>= median or < median; >= 25th percentile vs < 25th percentile; >= 75th percentile vs < 75th percentile);
- 9) Subjects grouped by baseline peripheral blood eosinophil count (< 150 Cells/UL vs >= 150; < 300 Cells/UL vs >= 300).

Unacceptable spirometry data based on "Valid Best Test Review Result" will be excluded from the above analyses.

Absolute measurement over time, change from baseline over time, and percent change from baseline over time by treatment group will be graphed for the following spirometry measurement for overall and subgroups and for ITT population and PP population: pre- and post-bronchodilator FEV_1 (L) and pre-bronchodilator FVC (L).

Summary	Population	Analysis
Summary of Spirometry Results	ITT	Stage 1; Stage 2

MedImmune

Tralokinumab

Version 2.0

Change from Baseline in Spirometry Results	ITT	Stage 1; Stage 2
Percent Change from Baseline in Spirometry Results	ITT	Stage 1; Stage 2
Summary of Home Peak Flow Testing	ITT	Stage 1; Stage 2
Change from Baseline in Home Peak Flow Testing	ITT	Stage 1; Stage 2
Percent Change from Baseline in Home Peak Flow Testing	ITT	Stage 1; Stage 2
Summary of Change from Baseline in Spirometry Results at Week 53	ITT	Stage 1
Summary of Change from Baseline in Spirometry Results at Week 75	ITT	Stage 2
Summary of Spirometry Results	РР	Stage 1; Stage 2
Change from Baseline in Spirometry Results	РР	Stage 1; Stage 2
Percent Change from Baseline in Spirometry Results	РР	Stage 1; Stage 2
Summary of Home Peak Flow Testing	РР	Stage 1; Stage 2
Change from Baseline in Home Peak Flow Testing	РР	Stage 1; Stage 2
Percent Change from Baseline in Home Peak Flow Testing	РР	Stage 1; Stage 2
Summary of Change from Baseline in Spirometry Results at Week 53	РР	Stage 1
Summary of Change from Baseline in Spirometry Results at Week 75	РР	Stage 2

3.6.3 The Effect of Tralokinumab on Patient Reported Outcomes

ACQ-6 is a shortened version of the ACQ that assesses asthma symptoms (night-time waking, symptoms on waking, activity limitation, shortness of breath, wheezing and short-acting $\beta 2$ agonist use). ACQ-6 will be completed weekly by using an ePRO device. Questions are weighted equally and scored from 0 (totally controlled) to 6 (severely uncontrolled). The mean ACQ-6 score is computed as the mean of the responses from all 6 items in the questionnaire. Mean ACQ-6 score ≤ 0.75 indicates well-controlled asthma, scores greater than

Version 2.0

0.75 and less than 1.5 indicates partly controlled asthma, and a score \geq 1.5 indicates uncontrolled asthma (Juniper et al, 2006). Individual changes of at least 0.5 are considered to be clinically meaningful (Juniper et al, 2005).

We intend to follow the guidelines established by Juniper (Elizabeth Juniper, Asthma Control Questionnaire -- Background Administration and Analysis, 2004, QoL Technologies). In order to be more specific, the exact algorithm that will be implemented in imputation of the missing data will be specified in the SPP. The mean ACQ-6 score along with the changes from baseline will be summarized using descriptive statistics. The proportions of subjects achieving mean ACQ-6 \leq 0.75 (well-controlled), 0.75< mean ACQ-6<1.5 (partly controlled), and mean ACQ-6 of \geq 1.5 at Week 53 and Week 75 will be evaluated using Fisher's exact test.

The AQLQ(S) is a 32-item questionnaire that measures the health related quality of life experienced by asthma patients (Juniper et al, 1999). The questionnaire comprises 4 separate domains (symptoms, activity limitations, emotional function, and environmental stimuli). Subjects are asked to recall their experiences during the previous 2 weeks and to score each of the 32 questions on a 7-point scale ranging from 7 (no impairment) to 1 (severe impairment). The overall score is calculated as the mean response to all questions. The 4 individual domain scores (symptoms, activity limitations, emotional function, and environmental stimuli) are the means of the responses to the questions in each of the domains. The minimal important difference (MID) for the AQLQ(S) total and domain scores is 0.5 (Juniper et al, 1994).

The overall and 4 domain scores from the AQLQ(S) responses along with their respective changes from baseline will be summarized using descriptive statistics by treatment group. Additionally, within each treatment group, the overall and 4 domain scores will be summarized by three categories, improvement (change in scores from baseline ≥ 0.5), no change (-0.5 \le change in score from baseline < 0.5), and worse (change in score < -0.5).

Mean ACQ-6 score over time and change from baseline in mean ACQ-6, overall AQLQ(s) score over time and change from baseline in AQLQ(s) over time will be plotted for overall and subgroups (see below) and for ITT population and PP population.

Subgroup analyses on ACQ-6 and AQLQ(s) will be conducted for the following subgroups:

- 1) Subjects with percentage of predicted FEV1 at baseline $\leq 60\%$, and $\leq 80\%$;
- 2) Subjects with baseline % FEV1 reversibility ($\geq 12\%$ and < 12%);

Version 2.0

- Subjects with FEV1 improvement at Week 5 and Week 13 (defined as percent change from baseline ≥ 10%) from tralokinumab group;
- 4) Subjects grouped by number of asthma exacerbations in the past year (2 vs > 2 but \leq 6 exacerbations);
- 5) Subjects grouped by chronic OCS use (presence vs absence);
- 6) Subjects grouped by Th2 status (Th2-high and Th2-low);
- 7) Subjects grouped by atopic asthma status (atopic vs. non-atopic);
- Subjects by serum baseline periostin level (>= median or < median; >= 25th percentile vs < 25th percentile; >= 75th percentile vs < 75th percentile);
- 9) Subjects grouped by baseline peripheral blood eosinophil count (< 150 Cells/UL vs >= 150; < 300 Cells/UL vs >= 300)

The EQ-5D will be completed at the site at Weeks 1 (Day 1), 13, 25, 41, 53, and 75. The questionnaire assesses 5 dimensions: mobility, self-care, usual activities, pain/discomfort, and anxiety/depression (EuroQol Group, 1990). Each dimension has 3 response options (no problem, some or moderate problems, and unable or extreme problems) that reflect increasing levels of difficulty. The respondent is asked to indicate his/her current health state by selecting the most appropriate level in each of the 5 dimensions. The questionnaire also includes a visual analog scale (EQ VAS), where the subjects are asked to rate their current health on a scale of 0-100, with 0 being the worst imaginable health state. The frequency and the proportion of subjects for each response level for each dimension will be reported by treatment group and by visit. The EQ VAS data will be summarized with descriptive statistics.

The ASMA Diary is a self-completed PRO instrument designed for once daily data capture using an electronic device (e-diary). The diary was developed by MedImmune and UBC to evaluate outcomes in patients aged 12 years and above with inadequately controlled moderate to severe persistent asthma. Each morning subjects are asked to recall their experience with daytime and nighttime symptom frequency and severity, activity avoidance and limitation, asthma-related anxiety and fatigue as well as rescue medication use.

There are three symptom questions in the ASMA diary: daytime frequency (question 1), daytime severity (question 2) and nighttime severity (question 6). All symptom questions are scored from zero to four, where a higher score indicates greater frequency or severity. Asthma symptom scores will be summarized weekly for subjects with at least 4 non-missing records each week. The baseline score should be calculated from day -7 to day -1. Change MedImmune

Tralokinumab

Version 2.0

from baseline tables will be assessed using descriptive statistics and created for daytime frequency, daytime severity, nighttime severity and overall symptoms ((daytime severity score + daytime frequency score + nighttime severity score)/3). Additionally, proportion of symptom-free days will be calculated (questions 1, 2, 5 and 6 = 0) and presented at weekly intervals from Week -4 until Week 75.

Scores for nighttime awakenings will be generated based on the single item (question 5) which has a dichotomous response option (YES/NO). Nighttime awakening will be summarized weekly for subjects with at least 4 non-missing records each week. The baseline score should be calculated with data from day -7 to day -1. Change from baseline tables will be assessed using descriptive statistics and created for the average number of awakenings per week.

Rescue medication use is collected from three questions: daytime use in response to symptoms (question 3), daytime prophylactic use (question 4) and nighttime use (question 7). Rescue medication use questions are first assessed using a dichotomous response option (YES/NO). If the subject reports YES, there is a subsequent question about the number of times rescue medication was used (questions 3a, 4a and 7a). Daily average scores should be summarized each week for all subjects with at least 4 non-missing records each week. Days with no reported rescue medication use should be represented as zero and included in the calculation with subjects that reported yes and completed questions 3a, 4a and 7a. The baseline score should be calculated from day -7 to day -1. Change from baseline tables will be created for daytime in response to symptoms, nighttime, prophylactic, total without prophylactic and total with prophylactic. Additionally, days without rescue medication use will be calculated (questions 3 and 7 = 0) and presented at weekly intervals from Week -4 until Week 75.

There are three activity limitation questions in the ASMA diary. All activity questions are scored from zero to four, where the higher score indicates greater limitation. Activity limitation scores will be summarized weekly for subjects with at least 4 non-missing records each week. The baseline score should be calculated from day -7 to day -1. Change from baseline tables will be assessed using descriptive statistics and created for overall activity limitation, avoiding activities and pacing during activities.

Summary	Population	Analysis
Summary of Mean ACQ-6 Scores	ITT	Stage 1; Stage 2

MedImmune

Tralokinumab

Version 2.0

Change from Baseline in Mean ACQ-6 Scores	ITT	Stage 1; Stage 2
Summary of Proportion of Subjects Achieving Mean ACQ-6 \leq 0.75, 0.75 <mean acq-6<1.5,="" acq-6<math="" mean="">\geq1.5 at Week 53</mean>	ITT	Stage 1
Summary of Proportion of Subjects Achieving Mean ACQ-6 \leq 0.75, 0.75 $<$ Mean ACQ-6 $<$ 1.5, Mean ACQ-6 \geq 1.5 at Week 75	ITT	Stage 2
Summary of AQLQ(S) Total and Domain Scores	ITT	Stage 1; Stage 2
Change from Baseline in AQLQ(S) Total and Domain Scores	ITT	Stage 1; Stage 2
Summary of AQLQ(S) Response (Improvement, No Change, and Worse)	ITT	Stage 1; Stage 2
Summary of EQ-5D Response	ITT	Stage 1; Stage 2
Change from Baseline in EQ-5D Response	ITT	Stage 1; Stage 2
Summary of EQ VAS Data	ITT	Stage 1; Stage 2
Change from Baseline in EQ VAS Data	ITT	Stage 1; Stage 2
Summary of EQ-5D Index	ITT	Stage 1; Stage 2
Change from Baseline in EQ-5D Index	ITT	Stage 1; Stage 2
Weekly Summary of ASMA Diary: Asthma Symptoms	ITT	Stage 1; Stage 2
Weekly Summary of ASMA Diary: Rescue Medication Use	ITT	Stage 1; Stage 2
Weekly Summary of ASMA Diary: Nighttime awakenings	ITT	Stage 1; Stage 2
Weekly Summary of ASMA Diary: Activity Limitation Scores	ITT	Stage 1; Stage 2
Change from Baseline in ASMA Diary: Asthma Symptoms	ITT	Stage 1; Stage 2

		-
Change from Baseline in ASMA Diary: Rescue Medication Use	ITT	Stage 1; Stage 2
Change from Baseline in ASMA Diary: Nighttime Awakenings	ITT	Stage 1; Stage 2
Change from Baseline in ASMA Diary: Activity Limitation Scores	ITT	Stage 1; Stage 2
Summary of Mean ACQ-6 Scores	РР	Stage 1; Stage 2
Change from Baseline in Mean ACQ-6 Scores	РР	Stage 1; Stage 2
Summary of Proportion of Subjects Achieving Mean ACQ-6 \leq 0.75, 0.75 <mean acq-6<1.5,="" acq-6<math="" mean="">\geq1.5 at Week 75</mean>	РР	Stage 2
Summary of AQLQ(S) Total and Domain Scores	РР	Stage 1; Stage 2
Change from Baseline in AQLQ(S) Total and Domain Scores	РР	Stage 1; Stage 2
Summary of AQLQ(S) Response (Improvement, No Change, and Worse)	РР	Stage 1; Stage 2
Summary of EQ-5D Response	РР	Stage 1; Stage 2
Change from Baseline in EQ-5D Response	РР	Stage 1; Stage 2
Summary of EQ VAS Data	РР	Stage 1; Stage 2
Change from Baseline in EQ VAS Data	РР	Stage 1; Stage 2
Summary of EQ-5D Index	РР	Stage 1; Stage 2
Change from Baseline in EQ-5D Index	РР	Stage 1; Stage 2
Weekly Summary of ASMA Diary: Asthma Symptoms	РР	Stage 1; Stage 2
Weekly Summary of ASMA Diary: Rescue Medication Use	РР	Stage 1; Stage 2
Weekly Summary of ASMA Diary: Activity Limitation Scores	РР	Stage 1; Stage 2

Change from Baseline in ASMA Diary: Nighttime Awakenings	РР	Stage 1; Stage 2
Change from Baseline in ASMA Diary: Activity Limitation Scores	РР	Stage 1; Stage 2

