2.1 Study Overview

This is a Phase 2b, randomized, double-blind, placebo-controlled, parallel-arm, multicenter study to evaluate the efficacy and safety of two SC treatment regimens of tralokinumab in adult subjects with uncontrolled, severe asthma requiring high-dose ICS and LABA with or without additional controller medications (high-dose ICS defined as a total daily dose $> 500 \mu g$ fluticasone DPI or $> 440 \mu g$ MDI; GINA, 2009; National Heart, Lung, and Blood Institute, 2007). Approximately 100 sites around the world will participate in the study. A total of approximately 390 subjects will be randomized in a 1:1 ratio to one of 2 cohorts (Cohort 1 or Cohort 2). Within each cohort, subjects will be randomized in a 2:1 ratio to receive tralokinumab (300 mg) or placebo as follows:

Cohort 1: Tralokinumab 300 mg (n = 130) or Placebo (n = 65) as 2 SC injections Q2W for 50 weeks for a total of 26 doses

Cohort 2: Tralokinumab 300 mg (n = 130) or Placebo (n = 65) as 2 SC injections Q2W for 12 weeks followed by Q4W for 38 weeks for a total of 16 doses

Subjects will be stratified at screening by the number of asthma exacerbations in the past 12 months (2 versus > 2 but \leq 6 exacerbations) and by chronic OCS use (presence versus absence). To maximize the probability of obtaining treatment balance within Japanese population for the purpose of PMDA filing, the Japanese will be randomized separately.

A 5-week screening/run-in period (Week -5 to -1 [Day -1) will precede investigational product administration. Starting at Week -4 (Day -28), subjects will receive a fixed-dose combination product of fluticasone/salmeterol, either as an MDI (230 μ g/21 μ g) at a dose of 2 inhalations twice per day or as a DPI (500 μ g/50 μ g) at a dose of one inhalation twice per day. Sites/subjects will be permitted to use either presentation of fluticasone/salmeterol if approved and available for use in their country. If the subject is also taking additional asthma controller medications (including leukotriene modifiers, theophylline, chromones, or OCS \leq 20 mg/day), then these medications should be continued at a stable dose during the screening/run-in period. During the study, subjects may use inhaled reliever therapy (e.g., SABA or short-acting anticholinergic) on an as-required basis as documented in their Personalized Asthma Action Plan.

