2.2 Randomization and Blinding

2.2.1 Subject Randomization Procedures and Treatment Allocation

An IXRS will be used for randomization to a cohort and assignment of blinded investigational product kit numbers. A subject is considered randomized into the study when the investigator or designee notifies the IXRS that the subject meets eligibility criteria and the IXRS provides the assignment of blinded investigational product kit numbers to the subject.

Subjects will be randomized in a 1:1 ratio to one of 2 cohorts. Within each cohort, subjects will be randomized in a ratio of 2:1 to receive SC tralokinumab (300 mg) or placebo. Subjects will be stratified at screening by the number of asthma exacerbations in the past year (2 versus > 2 but \leq 6 exacerbations) and by chronic OCS use (presence versus absence). To maximize the probability of obtaining treatment balance within Japanese population for the purpose of PMDA filing, the Japanese will be randomized separately.

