The accrual of asthma exacerbations is monitored during the study and blinded estimates of the annual asthma exacerbation rate in the placebo group are calculated. These estimates are consistently lower than the planned placebo rate of 1.2 exacerbations per year. In order to maintain adequate power to detect a 40% reduction in the annual asthma exacerbation rate for each tralokinumab cohort compared to placebo, the significance level for the data analysis will be raised from two-sided 0.1 to two-sided 0.15.

Sites in Japan will randomize approximately 65 Japanese subjects as part of the overall sample size. In the event that enrollment of the Japanese subjects is significantly delayed, and to ensure a timely Stage 1 analysis, non-Japanese sites may contribute sufficient subjects to reach the sample size required for the Stage 1 analysis (at least 390 subjects). In this event, sites in Japan will be permitted to continue enrollment until such time as approximately 65 Japanese subjects have been enrolled.

3 Statistical Methods

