3.1 General Considerations

Two formal analyses (Stage 1 analysis and Stage 2 analysis) as well as an interim analysis are planned for the study.

The Stage 1 analysis for the overall population will be conducted after the last non-Japanese subject has completed the Week 53 visit or discontinued prematurely (this analysis will include all Japanese subjects who have completed Week 53). The Stage 2 analysis for long-term safety follow-up will be performed after all subjects have completed the study or discontinued prematurely. During the Stage 1 analysis, all the efficacy and safety data

Version 2.0

collected will be analyzed. Pairwise comparisons between individual tralokinumab treatment groups and combined placebo will be conducted. The primary analysis for which the study is powered will be completed in the Stage 1 analysis, and the analyses based on primary efficacy endpoint will be repeated for overall population (which includes all subjects enrolled into the study) at the end of the study as sensitivity analysis.

The interim analysis will be conducted after the last non-Japanese subject randomized into the study has completed the Week 39 visit or discontinued prematurely. All data available will be analyzed as part of the interim analysis. The details of the interim analysis will be specified in unblinding plan for interim analysis.

The overall type I error rate (two-sided) will be controlled at the 0.15 level using O'Brien-Fleming alpha spending function based on the actual person-years follow-up observed. For example, if the information fraction at the interim analysis is 88%, then the two-sided type I error rate will be 0.105 for the interim analysis and 0.128 for final analysis, respectively. The interim analysis will have minimal impact on the power of the study at the final analysis, which is estimated to be approximately 78%.

Three sets of analyses will be performed at Stage 1. They are: 1) analyses based on overall population; 2) analyses for Japan only subjects (n=45); and 3) analyses for non-Japanese subjects. The go/no-go decision will be based on stage 1 analysis for overall population.

In addition, for PMDA consultation, the same analyses for all Japan subjects (n=64) will be conducted when all Japan subjects complete week 53 follow-up or discontinue prematurely.

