3.6 Summaries to Support the Secondary Objectives

The secondary objectives of this study are:

1) To evaluate the safety and tolerability of tralokinumab.

- 2) To evaluate the effect of tralokinumab on pulmonary function: clinic spirometry, including pre- and post-bronchodilator FEV1, FEV6, FVC, FEV1/FVC, IC; and PEF and FEV1 measured at home.
- 3) To evaluate the effect of tralokinumab on Patient Reported Outcomes: ACQ-6 score, HRQoL using AQLQ[S], and EQ-5D.
- 4) To evaluate the effect of tralokinumab on asthma symptoms and use of rescue medication using the ASMA diary.
- 5) To describe the pharmacokinetics (PK) and immunogenicity of tralokinumab.

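### ACQ-6 is tested only by Fisher's exact test on three control categories; a baseline-adjusted model of the mean score would add power and an effect estimate at almost no cost

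*SAP*

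**What the plan says.** SAP section 3.6 lists the ACQ-6 among the secondary objectives: "To evaluate the effect of tralokinumab on Patient Reported Outcomes: ACQ-6 score, HRQoL using AQLQ[S], and EQ-5D". Section 3.6.3 defines the score as the mean of six items, each scored 0 to 6, completed weekly. For the score itself it says: "The mean ACQ-6 score along with the changes from baseline will be summarized using descriptive statistics". It then cuts the score at 0.75 and 1.5 into well, partly and uncontrolled asthma, and says that the proportions in these categories "at Week 53 and Week 75 will be evaluated using Fisher's exact test".

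The rest of 3.6.3 adds plots, subgroup analyses and table titles for ACQ-6, but no model and no other test. Adjusted models appear elsewhere: a covariate-adjusted Poisson regression for exacerbations (3.5) and, as an option, ANCOVA on change from baseline for spirometry (3.6.2). Both include the two stratification factors.

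**The concern.** ACQ-6 is close to continuous and has a baseline. Fisher's test on the three categories uses only part of what is collected:

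- Movement within a category does not count. A patient going from 4.0 to 1.6 improves by 2.4 points and stays uncontrolled.
- The order of the categories is not used.
- Baseline ACQ-6 and the factors used to stratify randomisation (number of prior exacerbations and chronic OCS use, SAP 2.2.1) do not enter.
- The result is a p-value, with no adjusted mean difference and no confidence interval, although the SAP otherwise works with 85% intervals (3.1, 3.5).

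At stake is how precisely the trial can report a stated secondary objective.

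**Working it through.** **Inputs from the SAP.** Section 3.1: "Pairwise comparisons between individual tralokinumab treatment groups and combined placebo will be conducted". Section 2.1 gives 130 patients per tralokinumab regimen and 65 + 65 = 130 on combined placebo. On alpha, section 2.3 says: "the significance level for the data analysis will be raised from two-sided 0.1 to two-sided 0.15". The ACQ-6 cut points are those of 3.6.3.

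**Inputs that are assumptions.** The SAP states no ACQ-6 power, SD, mean, correlation or target difference, so there is no ACQ-6 figure to reproduce. Assumed: Week 53 placebo mean 1.5, 2.0 or 2.3; SD 1.0 or 1.2; baseline mean 2.5 with SD 1.0; baseline correlation r of 0.3, 0.5 or 0.6; mean difference 0.3 or 0.5; no missing data; no stratum effects. Scores were rounded to sixths and limited to 0-6. Fisher's test was taken as pairwise on a 2x3 table.

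**Hand check of one case** (placebo mean 2.0, SD 1.0, r = 0.5, difference 0.3, 130 per group).

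1. Category probabilities (well / partly / uncontrolled). With rounding to sixths, the boundaries on the underlying scale are 0.75 and 17/12 = 1.417. Placebo: Φ(0.75 - 2.0) = 0.106, Φ(1.417 - 2.0) = 0.280, giving 10.6% / 17.4% / 72.0%. Active (mean 1.7): 17.1% / 21.7% / 61.2%.
2. Unordered test, chi-square approximation on 2 df: noncentrality = (130/2) × Σ(difference²/mean proportion) = 3.78; critical value at 0.15 = 3.79; power 61%.
3. Unadjusted test on the score: SE = √(2/130) = 0.124; power = Φ(0.3/0.124 - 1.440) = 84%.
4. ANCOVA: SE = 0.124 × √(1 - 0.5²) = 0.107; power = Φ(0.3/0.107 - 1.440) = 91%. The 85% CI would be the estimate ± 1.440 × 0.107 = ± 0.15 points.

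Simulation of the same case (1,500 trials) gives Fisher 60%, t-test 83% and ANCOVA 91%, in agreement.

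**Simulated power, 130 per group, two-sided 0.15, difference 0.3** (all 18 combinations of mean, SD and correlation):

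| Test | Power |
|---|---|
| Fisher's exact, three categories | 45-66% |
| Trend test, same categories | 54-76% |
| t-test on the score | 69-85% |
| ANCOVA with baseline | 73-95% |

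From Fisher to ANCOVA the loss is 20-40 points, median about 30. Case by case it splits into 7-10 points from ignoring order, 7-22 from categorising, and 1-14 from leaving out baseline.

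**Difference 0.5.** At r = 0.5 and 130 per group, Fisher has 82-96% and ANCOVA above 99%, a loss of 4-17 points. Allowing r from 0.3 to 0.6 and 115-130 per group widens this to about 4-20.

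**Fewer evaluable patients.** A separate simulation used 115 per group, placebo mean 1.85, baseline mean 2.6 with SD 0.8, and r = 0.5. For 0.3 points, Fisher had 57% (SD 1.0) and 46% (SD 1.2), against 87% and 77% for ANCOVA. For 0.5 points, Fisher had 92% and 81%, against more than 97%.

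**No effect.** Fisher rejects in 14-16% of trials at the 0.15 level, so type I error is not at issue.

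**The case against.** The strongest reply is that nothing here is wrong. Fisher's test is valid, the study is powered only on the exacerbation rate, no decision rule rests on ACQ-6, and AQLQ(S), EQ-5D and the ASMA diary get no between-arm test at all. This stands, and it is why the point is an improvement and not a correction.

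Four stronger readings are tempting, and the SAP does not support them:

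- *A flat loss of 30 points.* That is a middle value for an assumed 0.3-point difference. The only ACQ-6 benchmark in the SAP is 0.5, for change in an individual and not for a difference between group means. At a 0.5-point mean difference the loss is much smaller.
- *A real benefit would probably be missed.* Fisher's power of about 45-66% at 0.3 points is roughly even odds, and it is higher for larger effects.
- *A significant result would leave the direction unknown.* The test on a 2x3 table does not assess direction, but the proportions are tabulated by group, and mean change is summarised and plotted, so a reader would see it. The wording could also mean one 2x2 test per category, which has a direction. Power is then similar (42-59% at 0.3 points), so the loss remains.
- *Ignoring the strata accounts for part of the loss.* Stratum effects were not simulated. ACQ-6 is also analysed in subgroups defined by both stratification factors, though that is not adjustment.

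**Conclusion.** The point holds as a nearly free gain in efficiency. The structural part needs no assumptions: the only between-arm test named for ACQ-6 discards the score within categories, their order and the baseline, and yields no adjusted difference with an interval. The size does rest on assumptions (Week 53 placebo mean 1.5-2.3, SD 1.0-1.2, baseline correlation 0.3-0.6, 115-130 per group, two-sided 0.15): about 20-40 points of power for a 0.3-point difference and about 4-20 for 0.5. Categorising has the largest upper range of the three components. It would be wrong to infer that the planned test is invalid or that any planned conclusion of the trial depends on it.

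**What to change.** In 3.6.3, prespecify the ACQ-6 comparison as change in mean ACQ-6 at Week 53, each tralokinumab regimen against combined placebo. Use ANCOVA or a repeated-measures model on the weekly scores, with treatment, baseline ACQ-6, prior exacerbations (2 versus more than 2), chronic OCS use and region. Report the estimated difference with its 85% CI.

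Keep the three categories as supportive description, or analyse them with a proportional-odds model with the same covariates. Changing only the category test is not enough: in the simulations, a trend test on the same categories without covariates recovered only 7-10 points.

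The cost is a few sentences in the SAP and one more model on data already collected.
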